3.3.4.2 Discontinuation of the trial by the sponsor

Boehringer Ingelheim reserves the right to discontinue the trial overall or at a particular trial site at any time for the following reasons:

1	Failure to meet expected enrolment goals overall or at a particular trial site
2	Emergence of any efficacy/safety information invalidating the earlier positive benefit-risk assessment that could significantly affect the continuation of the trial.
3	Violation of GCP, the CTP or the contract disturbing the appropriate conduct of the trial
4	New toxicological findings or serious adverse events invalidate the earlier positive benefit-risk assessment. More specifically, the trial will be terminated if two subjects have, at least, possibly related SAE or in case of the occurrence of three, at least, possibly related severe AEs. No further dosing, dose escalation or inclusion of any further

Proprietary confidential information © 2017 Boehringer Ingelheim International GmbH or one or more of its affiliated companies

	subjects (independent of dose level) will occur without approval of a substantial amendment.
5	
Part 1 (pilot study): At least 2 subjects* in the current cohort or treatment period on active drug showed serum potassium levels $\geq 5.5\text{mmol/L}$ in non-haemolysed blood (confirmed by repeat).
 
Part 2 (main study): At least 4 subjects* on active drug (independent of dose level) showed serum potassium levels $\geq 5.5\text{mmol/L}$ in non-haemolysed blood (confirmed by repeat).
 
* These are proposed thresholds for potential trial discontinuation however any and all individual occurrences of serum potassium levels $\geq 5.5\text{mmol/L}$ in non-haemolysed blood will be reviewed by the PI and sponsor medical team.

6	
At least 2 subjects independent of dose level on active drug showed relevant individual QT prolongation, i.e. a QTcF increase of greater 60 ms from baseline in connection with absolute QT or QTcF greater than 500 ms, which has been confirmed by a repeat ECG recording*
 
*These are proposed thresholds for potential trial discontinuation however any and all individual occurrences of QT prolongations will be reviewed by the PI and sponsor medical team

The Investigator / trial site will be reimbursed for reasonable expenses incurred in case of trial termination (except in case of the third reason).

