he most sensitive species for these effects was the rat with no relevant effects observed in the dog, even at high doses, on serum or urinary electrolytes. No other systemic safety findings were observed in either the toxicology or safety pharmacology studies.

This translates to a safety margin of approximately 11-fold. The urine cover is regarded as the most relevant exposure for safety based mechanism i.e. serum electrolytes.

BI 443651 does not present a genotoxic hazard. BI 443651 is considered to be low risk for phototoxicity, based on its absorbance pattern and lack of toxicity in 4-week repeat dose studies.

Fertility has not been assessed in nonclinical species, but no adverse effects have been observed on reproductive organs in 4-week toxicity studies in rats and dogs, suggesting that there is a low risk to fertility. At the time this current study is planned to start embryo-fetal development studies of BI 443651 will not yet have been conducted.

Off target inhibition of ACh has been observed with augmented effects in non-clinical ACh/MCh challenge guinea pig models. No adverse effects on pulmonary function were observed in the absence of methacholine or acetylcholine challenge. No adverse respiratory effects were detected in the 4-week toxicology studies or in the safety pharmacology studies at doses of up to 7,750 µg/kg in dog or rat. Exaggerated bronchoconstriction effects may be apparent following methacholine challenge however effects on respiratory function will be monitored and are reversible. Inhaled anticholinergic therapy should reverse these effects if required, as is also used if required for MCh testing.

In summary whilst not all safety effects may be predicted, based on mechanism and systemic toxicological finding the only potential systemic toxicity is changes in serum electrolytes and

Proprietary confidential information © 2017 Boehringer Ingelheim International GmbH or one or more of its affiliated companies

particularly increases in serum potassium. Augmented bronchoconstriction may be induced following administration of methacholine. In both cases these changes are easily monitored and treatable if observed. The following safety measures will be applied in this study in order to minimize the risk for the mild asthmatic subjects:

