- 1 This study (1363.7) will only start once healthy volunteers have been safely administered 100 and 400 µg b.i.d. of BI 443651 for 7days in a separate ongoing study (1363.2) i.e. no stopping criteria have been triggered in 1363.2.
- 2 Only mild, controlled, stable asthma subjects with well-maintained lung function will be included in the study i.e. subjects on prn SABA or low dose inhaled corticosteroid with an $FEV_1 \geq 70\%$ and no recent respiratory tract infection or exacerbation.
- 3 The study will be split into two parts ([see Section 3.1](#)) with an initial pilot (Part 1) to assess for gross adverse effects of BI 443651 on bronchoconstriction after MCh challenge. In Part 1, subjects will receive BI 443651 in a dose ordered fashion with either placebo **or** the lowest dose first followed by the higher doses and placebo (if not taken first). Individual subjects will not be dosed further if individual stopping criteria (including pulmonary function criteria) are triggered. Stopping criteria are described in detail in [Section 3.3.4](#).

The second part of the study (not necessarily dose ordered) will only proceed if no subjects triggered the first three discontinuation criteria following administration of BI 443651 during Part 1.

- 4 The subjects will be closely monitored throughout the treatment period with frequent evaluation of pulmonary function following MCh challenge. Subjects may only be discharged from clinic after medical assessment has been conducted. The subject's FEV_1 must have returned to $\geq 90\%$ of the first set of spirometry measurements performed that day before the subject can be discharged from the clinic. Rescue medication will be provided as required.
- 5 Safety laboratory testing will be performed during the study with a focus on electrolytes ([see Flow Chart](#)). The study will be stopped if, during Part 1 (pilot) at least 2 subjects in the current cohort or treatment period on active drug showed serum potassium levels $\geq 5.5\text{mmol/L}$ in non-haemolysed blood (confirmed by repeat). In Part 2 (main study), the study would be stopped if 4 subjects on active drug (independent of dose level) showed serum potassium levels $\geq 5.5\text{mmol/L}$ in non-haemolysed blood (confirmed by repeat).

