4.1.5 Blinding and procedures for unblinding

4.1.5.1 Blinding

In the pilot part of the study (Part 1), site staff dosing the subjects will be unblinded. Unblinded site staff will not conduct any study assessments.

The main part of the study (Part 2) will be double-blind and subjects, investigators and everyone involved in trial conduct or analysis or with any other interest in this trial will remain blinded with regard to the randomised treatment assignments until after database lock.

The randomisation code will be kept secret by Clinical Trial Support up to database lock.

The randomisation codes will be provided to bioanalytics prior to the last subject out date to allow for the appropriate analyses of pharmacokinetic (PK) samples taken from different dose strengths. Bioanalytics will not disclose the randomisation code or the results of their measurements until the trial is officially unblinded.

The trial will only be unblinded after locking of the database.

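### In Part 2 the potassium and QT discontinuation thresholds count only subjects on active drug, but the people who review the cases are blinded and neither document links code access to that count

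*Protocol*

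**What the plan says.** Protocol section 3.3.4.2 lists the reasons for which the sponsor may discontinue the trial.

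- Reason 5, potassium: "Part 2 (main study): At least 4 subjects* on active drug (independent of dose level) showed serum potassium levels" at or above 5.5 mmol/L in non-haemolysed blood, confirmed by repeat.
- Reason 6, QT: "At least 2 subjects independent of dose level on active drug showed relevant individual QT prolongation", also confirmed by repeat.
- The potassium footnote reads "These are proposed thresholds for potential trial discontinuation however any and all individual occurrences of serum potassium levels" at or above that limit go to the principal investigator and the sponsor's medical team for review. The QT footnote has the same effect.
- Reason 4, by contrast, is firm and depends on judged relatedness: "the trial will be terminated if two subjects have, at least, possibly related SAE", or if three severe events of that kind occur.

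Section 2.3 introduces its list with "The following safety measures will be applied in this study in order to minimize the risk for the mild asthmatic subjects". On potassium in Part 2 that list says "the study would be stopped if 4 subjects on active drug (independent of dose level) showed serum potassium levels" at or above the limit. The same section explains why potassium matters: "the only potential systemic toxicity is changes in serum electrolytes", with increases in potassium singled out.

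On blinding in Part 2, section 4.1.5.1 says that subjects, "investigators and everyone involved in trial conduct or analysis or with any other interest in this trial will remain blinded" until after database lock.

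**The concern.** Whether a case counts towards reason 5 or 6 depends on the treatment the subject was receiving. In Part 2 the people named as reviewers may not know that. Followed exactly, the two rules leave a stated safety threshold whose status cannot be determined while the trial is running.

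The potassium threshold is offered in the benefit-risk section as protection against the one systemic toxicity the sponsor expects. A reader of 2.3, such as an ethics committee, would take it to be a working and binding rule. Section 3.3.4.2 makes it advisory, and 4.1.5 leaves nobody assigned to tell the reviewers when it is met.

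**Working it through.** **1. Routes to the code in Part 2**

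- Clinical Trial Support holds the randomisation code and keeps it secret until lock (4.1.5.1).
- Bioanalytics receives the codes early but may not disclose them before official unblinding (4.1.5.1).
- Pharmacovigilance may see individual codes for SUSAR reporting but may not pass them on (4.1.5.2).
- Emergency envelopes may be opened to treat a subject or to secure participants' safety, but only in an emergency. Opening one is not tied to these thresholds (4.1.5.2).
- The unblinded staff who prime the inhalers take no part in trial conduct and have no reporting task (4.1.4).
- The safety reviews in 3.1 cover dose escalation in Part 1, the move to Part 2 and unscheduled meetings. None grants access to the code.
- Neither document names a data monitoring committee.

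No route is linked to the count.

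**2. What the blinded total shows**

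Total cases = active cases + placebo cases, so the total is never below the active count. The active-drug threshold therefore cannot be crossed before the reviewers have seen four potassium cases or two QT cases.

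**3. What it does not show**

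Inputs: three of each subject's four periods are active (3.1, Table 3.1:2). A subject counts once, because a confirmed case leads to withdrawal (3.3.4.1, criteria b and c). The documents give no event rates, so the active-to-placebo risk ratio per period, r, is assumed. For rare events the share of cases on active drug is a = 3r/(3r+1). The chance that all of the first n cases are on active drug is aⁿ. With one more case, the chance that at least n of n+1 are on active drug is (n+1)aⁿ(1−a) + aⁿ⁺¹.

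| r | a | Potassium: 4 of 4 active (a⁴) | At least 4 of 5 | QT: 2 of 2 active (a²) | At least 2 of 3 |
|---|---|---|---|---|---|
| 1 | 0.75 | 0.316 | 0.633 | 0.5625 | 0.844 |
| 3 | 0.90 | 0.656 | 0.919 | 0.810 | 0.972 |
| 5 | 0.9375 | 0.772 | 0.966 | 0.879 | 0.989 |

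A simulation of 32 subjects on the Table 3.1:2 sequences, with withdrawal at the first case and an assumed placebo rate of 1% per period (60,000 runs), agrees: 0.319, 0.654 and 0.774 for potassium; 0.562, 0.813 and 0.879 for QT. At the threshold number the blinded total does not settle the question. A case or two later it largely does.

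**4. How much earlier an all-treatment count would trigger**

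If cases keep arising, the mean number of total cases needed for four active ones is 4/a = 5.33, 4.44 and 4.27 for r = 1, 3 and 5. Counting every case therefore triggers on average 1.33, 0.44 and 0.27 cases sooner. For QT, 2/a = 2.67, 2.22 and 2.13, so it triggers 0.67, 0.22 and 0.13 cases sooner.

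**5. Whether the potassium threshold is likely to matter**

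With 32 subjects, no replacements and an assumed rate p per active period, the number of subjects with a case on active drug is Binomial(32, 1−(1−p)³). The chance of at least four is 0.014, 0.116 and 0.688 for p = 1%, 2% and 5%.

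**The case against.** The strongest reply is that 3.3.4.2 only reserves a right to stop. A discretionary threshold does not need a certified active-only count. The sponsor sees every case, can act on the blinded total, and can stop under reason 2 (new safety information) or reason 4, neither of which needs the code. All of this stands. What remains is that the protocol does not say the sponsor will act on the blinded total, and that 2.3 describes the potassium rule as a stop.

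A second reply is that code access is not fully closed. The emergency envelope extends to securing participants' safety, and the sponsor must be told when one is opened. Section 3.1.1 leaves trial tasks to sponsor SOPs, which are not available here and may assign the count. Section 3.3.5 gives a Part 2 replacement the same sequence as the subject replaced, a sequence-linked step that 4.1.5 does not mention, so silence there is weak evidence. This also stands: the documents support saying that no route is linked to the count, not that no route could exist. An SOP would still have to fit with a protocol that tells the code holder to keep the code secret and states no exception for this purpose.

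Third, the rule may never come into play. Potassium above the upper limit of normal bars entry (3.3.3), and single doses up to 3600 µg gave no clinically relevant laboratory or ECG abnormality (1.2.6). That lowers the weight of the point but does not make the rule operable.

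**Conclusion.** The point holds as a minor-to-moderate issue of operability in Part 2. As written, the reviewers can see when the active-drug threshold may have been reached but have no stated way to learn whether it has. For potassium, the two sections also disagree on whether the rule binds.

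A reader might infer that subjects are left unprotected, or that a threshold could pass unnoticed. The documents do not support either. Confirmed cases are withdrawn on any treatment, every case is reviewed, and the blinded total cannot lag the active count. A reader might also infer that a mandatory stop would be breached; 3.3.4.2 makes both thresholds advisory, and only 2.3, on potassium, says otherwise.

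The point is confined to Part 2, because the blinding of investigators until lock is stated for that part and Part 1 is single-blind. The textual conflict needs no assumption beyond the absence of an SOP that resolves it. The probabilities rest on assumed risk ratios and event rates and are illustrations only.

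**What to change.** In 3.3.4.2, state the Part 2 thresholds as the number of subjects with a confirmed case regardless of treatment: four for potassium, two for QT. Reaching either should trigger a pause in dosing and a documented safety review. This needs no code and cannot trigger later than the present rule. Give the potassium threshold the same status, binding or advisory, in 2.3 and 3.3.4.2. The threshold values remain the sponsor's choice.

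Optionally, let Clinical Trial Support tell the review only whether the active-drug threshold has been reached, with no individual codes released, and amend 4.1.5 to allow this.

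Costs: a protocol amendment, which under 8.1 needs ethics committee and authority approval before use. A review may come somewhat earlier because placebo cases count (step 4). If the optional check is used, a positive answer at the first check implies that all those cases were on active drug, though not at which dose. No extra visits, samples or staff are needed.

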3.3.5 Replacement of subjects

A 'completed' subject is defined as a subject who has completed all treatment periods and procedures including MCh challenge. Subjects who do not complete all treatment periods must be replaced. A replacement subject will be assigned a unique study subject number. In part I of the study, the replacement subject will only undergo the treatment periods not completed by the subject he/she replaces. In part II of the study, a replacement subject will be assigned to the same treatment sequence as the subject he/she replaces. The method to include these replacement patients in the analysis will depend on the time point of inclusion of the new patient in the study.

4 TREATMENTS

4.1 INVESTIGATIONAL TREATMENTS

The study medication below will be supplied by Boehringer Ingelheim Pharma GmbH & Co. KG

1 mg BI 443651 (MW 571.12 g/mol) equals 1.26 mg BI 443651 salt form (MW 721 g/mol). The doses given below refer to the respective free base.

4.1.1 Identity of the Investigational Medicinal Products

Table 4.1.1: 1 Test product 1

Substance:	BI 443651
Pharmaceutical formulation:	Solution for inhalation
Source:	BI Pharma GmbH & Co. KG, Germany
Unit strength:	100µg/actuation, 300µg/ actuation
Posology:	Depending on dose group
Route of administration:	Oral inhalation
Device:	RESPIMAT A5
Duration of use:	Multiple dose

Table 4.1.1: 2 Test product 2

Substance:	Placebo
Pharmaceutical formulation:	Solution for inhalation
Source:	BI Pharma GmbH & Co. KG, Germany
Unit strength:	Not applicable
Posology:	Depending on dose group
Route of administration:	Oral inhalation
Device:	RESPIMAT A5
Duration of use:	Multiple dose

For exact amounts and units to be administered per treatment and trial part please refer to [Section 4.1.4.](#)

4.1.2 Selection of doses in the trial

Orally inhaled doses in the range of 100 µg to 1200 µg have been selected in order to assess the safety, tolerability and pharmacokinetics of BI 443651 in asthma subjects. The doses were selected as follows ([C02337864](#)):

In the pilot study (Part 1), the investigator can decide at any time to discontinue dosing or to decrease the dose escalation by adding intermediate doses in case of intolerance or due to safety concerns. The site will follow relevant local SOPs.

4.1.3 Method of assigning subjects to treatment groups

Subjects are randomised to a treatment sequence at Visit 2 (i.e: Treatment Period 1). After assessment of all inclusion and exclusion criteria, each eligible subject will be assigned the lowest available medication number at the time of randomisation. Note that the medication number is different from the subject number (the latter is assigned directly after informed consent was obtained). Site personnel will enter the medication number in the eCRF.

Proprietary confidential information © 2017 Boehringer Ingelheim International GmbH or one or more of its affiliated companies

4.1.4 Drug assignment and administration of doses for each subject

The treatments to be evaluated are administered as outlined in Table 4.1.4:1 below.

Table 4.1.4: 1 Treatment overview

Treatment	Formulation, dose regimen	Treatment Administration*					Posology distribution over the treatment period
		Route	Number of actuations	Unit strength [µg]	Total dose [µg]	Total no. of placebo	
1 (100 µg)	Inhalation solution, three administrations 12 hours apart	Oral inhalation	1	100	100	3	Day 1: a.m. and p.m. Day 2: a.m. only
2 (400 µg)	Inhalation solution, three administrations 12 hours apart	Oral inhalation	4	100	400	0	Day 1: a.m. and p.m. Day 2: a.m. only
3 (1200µg)	Inhalation solution, three administrations 12 hours apart	Oral inhalation	4	300	1200	0	Day 1: a.m. and p.m. Day 2: a.m only
Placebo	Inhalation solution, three administrations 12 hours apart	Oral inhalation	-	-	-	4	Day 1: a.m. and p.m. Day 2: a.m only

*Four separate devices will be used in each treatment administration to maintain blinding. Placebo devices will be used to make a total of four administrations per dosing.

Proprietary confidential information © 2017 Boehringer Ingelheim International GmbH or one or more of its affiliated companies

Each newly assembled RESPIMAT Inhaler has to be primed by qualified, trained, unblinded study personnel, e.g. pharmacist at the trial site under the responsibility of the investigator, who is not involved in the conduct of the trial. Except those devices used for training, priming should NOT take place in the same room where the subject is inhaling trial medication

The inhaler should be primed by actuating it until an aerosol is visible plus three additional actuations. For detailed priming instructions please refer to the RESPIMAT Inhaler handling instructions in [Appendix 10.1](#).

Both the study drug as well as the placebo treatment (depending on randomisation) will be inhaled with the RESPIMAT in a sitting or standing position under supervision of the investigating physician or an authorised designee (see [section 4.3](#)). Inhalation of study drug should NOT take place in the same room where the blood samples are taken, to prevent contamination of samples from airborne drug. If more than one actuation is needed, planned time 0:00h will always be the first actuation. If more than one actuation will be needed, the duration from first to last actuation will be recorded. After study drug inhalation, subjects will drink 250 mL of water.

The so-called four-eye principle (two-person rule) should be applied for administration of trial medication and – if applicable – its preparation (e.g. assembling of device), if correct dosage cannot be ensured otherwise.

4.1.5 Blinding and procedures for unblinding

4.1.5.1 Blinding

In the pilot part of the study (Part 1), site staff dosing the subjects will be unblinded. Unblinded site staff will not conduct any study assessments.

The main part of the study (Part 2) will be double-blind and subjects, investigators and everyone involved in trial conduct or analysis or with any other interest in this trial will remain blinded with regard to the randomised treatment assignments until after database lock.

The randomisation code will be kept secret by Clinical Trial Support up to database lock.

The randomisation codes will be provided to bioanalytics prior to the last subject out date to allow for the appropriate analyses of pharmacokinetic (PK) samples taken from different dose strengths. Bioanalytics will not disclose the randomisation code or the results of their measurements until the trial is officially unblinded.

The trial will only be unblinded after locking of the database.

4.1.5.2 Unblinding and breaking the code

An emergency code break (envelope) will be available to the Investigator / pharmacist / investigational drug storage manager. This code break may only be opened in an emergency situation when the identity of the trial drug must be known to the Investigator in order to provide appropriate medical treatment or otherwise assure safety of trial participants. If the

Proprietary confidential information © 2017 Boehringer Ingelheim International GmbH or one or more of its affiliated companies

code break for a subject is opened, the sponsor must be informed immediately. The reason for opening the code break must be documented on the envelope and/or appropriate CRF page along with the date and the initials of the person who broke the code.

Due to the requirements to report Suspected Unexpected Serious Adverse Reactions (SUSARs), it may be necessary for a representative from Boehringer Ingelheim's Pharmacovigilance group to access the randomisation code for individual subjects during trial conduct. The access to the code will only be given to authorised Pharmacovigilance representatives and not be shared further.

